8.3.2.2 Use of Immunoglobulin Replacement Therapy

The number (%) of subjects receiving immunoglobulin replacement therapy will be summarized by visit.

The time to cessation of Ig RT will be calculated (in months), using the stop date on the concomitant medication form, as:

$$12 * (\text{stop date of Ig RT} - \text{date of infusion}) / 365.25.$$

Time to cessation of IgRT will be summarized using descriptive statistics and, if appropriate, estimated from a Kaplan-Meier curve in which subjects who are still receiving IgRT will be censored at the time of their last visit.

The number (%) of subjects who have stopped treatment with IgRT at 12, 18 and 24 months without restarting at any subsequent time point will be summarized.

In addition, serum immunoglobulin levels (IgG, IgA and IgM) will be measured at each visit. Levels of IgG, IgA and IgM and changes from baseline will be summarized by visit using descriptive statistics. In addition, plots of the median value and range over time on a logarithmic scale will be produced for each parameter along with individual plots for each subject which will include age-dependent normal ranges provided by the study site.

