For subjects who have successfully received the OTL-101 product, PEG-ADA ERT use will be evaluated at the 1 Month follow-up visit (30 days post treatment ± 7 days) and discontinued at Day 30 (-3/+15) after the transplant. Hematologic reconstitution will be assessed at Day 42 (± 7 days), and in the event of no reconstitution the backup HSC sample will be administered, if the investigator believes this is in the subject's best interest. The subjects will then be seen at regular intervals to review their history, perform examinations and draw blood samples at Months 3, 6 and 9 (all ± 2 weeks) as well as Months 12, 18 and 24 (all ± 4 weeks). Any medically-indicated interventions, including the need to reinstate PEG-ADA ERT, will be assessed at all follow-up visits after Month 1. Hematopoietic reconstitution will be assessed again at the Month 6 visit and if there is still no evidence of cellular recovery, the subject will be given ERT and/or HSCT, if available and deemed appropriate by the Investigator. After the Month 24 visit, the subjects will have completed the study and may enter a long term registry.

This study will include three statistical analyses:

1. The first analysis will compare the success/failure data 6-months post OTL-101 infusion between fresh and cryopreserved OTL-101 formulations. The success/failure of OTL-101 will be defined by the three criteria listed in the primary objectives ([Section 2.2.1](#)). This data will be compared with available data from one of the ongoing Phase I/II studies using the OTL-101 fresh formulation. This will support the CMC comparability data between OTL-101 cryopreserved and fresh formulations. Secondary and exploratory endpoints will also be described.
2. The second analysis will determine the 12 month overall survival and event free survival for all subjects. Secondary and exploratory endpoints, as well as baseline characteristics, subject disposition, and safety data will also be described.
3. The third and final analysis will be performed to determine the overall survival and event free survival for all subjects 24 months post OTL-101 infusion. Secondary and exploratory endpoints, as well as baseline characteristics, subject disposition, safety and Busulfan pharmacokinetic (PK) data will also be described.

Efficacy analyses will be primarily descriptive in nature.

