8.3.3 Exploratory Efficacy Endpoints

8.3.3.1 Use of PEG-ADA Enzyme Replacement Therapy

The time to withdrawal of PEG-ADA ERT will be calculated (in months), using the stop date on the concomitant medication form, as:

$$12^*(\text{stop of PEG-ADA ERT} - \text{date of infusion})/365.25.$$

Time to withdrawal of PEG-ADA ERT will be summarized using descriptive statistics and, if appropriate, estimated from a Kaplan-Meier curve in which subjects who are still receiving PEG-ADA ERT will be censored at the time of their last visit.

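### The only mandatory summary of time to stopping immunoglobulin replacement covers stoppers only, so it is too short whenever some children have not stopped

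*SAP*

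**What the plan says.** IgRT use is a secondary endpoint (SAP 5.2; Protocol 7.1.2). SAP 8.3.2.2 computes time to cessation as 12 × (stop date − infusion date)/365.25, "using the stop date on the concomitant medication form". The summary rule is: "Time to cessation of IgRT will be summarized using descriptive statistics and, if appropriate, estimated from a Kaplan-Meier curve". In that curve, "subjects who are still receiving IgRT will be censored at the time of their last visit". Nothing says when the curve counts as appropriate, and no rule gives a child without a stop date a value in the descriptive statistics.

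The same section has two summaries that do not depend on having stopped:
- "The number (%) of subjects receiving immunoglobulin replacement therapy will be summarized by visit"
- "The number (%) of subjects who have stopped treatment with IgRT at 12, 18 and 24 months without restarting at any subsequent time point"

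SAP 8.3.3.1 uses parallel wording for PEG-ADA, an exploratory endpoint: "Time to withdrawal of PEG-ADA ERT will be summarized using descriptive statistics and, if appropriate, estimated from a Kaplan-Meier curve".

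Two other provisions matter. SAP 5.1 withdraws subjects who fail the month-6 response criteria. SAP 6 says that secondary endpoints will be compared with the fresh-formulation study at the first analysis.

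**The concern.** A statistic computed only on children who have a stop date selects on the outcome. Slow or failed recovery removes a child from the calculation instead of lengthening the reported time. The figure can therefore stay much the same while the share of children who become independent of IgRT falls.

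The optional curve has a problem of its own. Censoring a child at the last visit assumes that the child could still stop at the same rate as those who remain. That is doubtful for a child withdrawn because treatment failed.

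What is at stake is how one descriptive secondary result reads, on its own and beside the fresh-formulation data. A stop time among stoppers cannot exceed follow-up. If the two cohorts were summarised over different lengths of follow-up, their stop-time medians would differ for that reason alone. The SAP does not say how the fresh data would be cut, so this is a possibility and not a finding.

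**Working it through.** **Inputs from the documents.** Ten treated subjects, enrolled at three to six per year (Protocol 9.4). Follow-up is 24 months (Protocol 3.5). The second analysis takes place when all subjects have 12 months of follow-up (SAP 6). The formula and censoring rule are in SAP 8.3.2.2.

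**Not in the documents.** No expected IgRT stopping rate or time is given. All stop times below are assumptions.

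**The plan's own figure.** The only precision figure is 15% for 10 of 10 (Protocol 9.4), and it concerns survival. The exact lower limit is 0.025^(1/10) = 0.6915, and the half-width is (1 − 0.6915)/2 = 15.4%, so it reproduces. There is no corresponding figure for time to stopping.

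**Step 1: fixed pattern.** Let k of 10 children stop at times evenly spaced over months 6 to 22, with the rest still on IgRT at month 24. The mean and median of the stop dates are (6 + 22)/2 = 14.0 months for every k. With all ten kept in:

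| k stopping | Stop-date median | Kaplan-Meier median | Mean time on IgRT to month 24 |
|---|---|---|---|
| 10 | 14.0 | 14.0 | 14.0 |
| 9 | 14.0 | 15.0 | 15.0 |
| 8 | 14.0 | 16.3 | 16.0 |
| 7 | 14.0 | 18.0 | 17.0 |
| 6 | 14.0 | 20.4 | 18.0 |
| 4 | 14.0 | not reached | 20.0 |

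For k = 7, the fifth and sixth stops fall at 16.7 and 19.3 months, with midpoint 18.0. The restricted mean is (7 × 14 + 3 × 24)/10 = 17.0.

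**Step 2: random stop times.** Assume Weibull times with shape 2 and true median M. The chance of stopping by month 24 is 1 − 0.5^((24/M)²). The table shows the simulated average of the median among stoppers for ten subjects. The range at the 12-month analysis covers entry at 3 to 6 per year.

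| True median (months) | 12-month analysis | Shortfall | Final analysis | Shortfall |
|---|---|---|---|---|
| 9 | 8.6 to 8.8 | 2% to 4% | about 9.0 | about 0% |
| 12 | 10.5 to 10.9 | 9% to 13% | 11.5 | 4% |
| 18 | 12.5 to 13.4 | 26% to 31% | 14.2 | 21% |
| 24 | 13.4 to 14.3 | 40% to 44% | 15.2 | 37% |

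A direct check for M = 18: the chance of stopping by month 24 is 0.708. The large-sample median among stoppers is where the cumulative probability equals 0.354, that is 18 × √(log2(1/0.646)) = 14.3 months, which agrees with the simulated 14.2.

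The result depends on the assumed shape. With exponential times at the final analysis, true medians of 12 and 24 months give 8.5 and 10.3 months, shortfalls of 29% and 57%. The Weibull range is an illustration and not a bound.

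**Step 3: the optional curve.** Suppose j children are withdrawn at month 6 while on IgRT, nobody has stopped before then, and 7 others stop later. Censoring the j gives an estimated proportion stopped of 7/(10 − j):
- j = 1: 7/9 = 78%
- j = 2: 7/8 = 88%

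Of all those treated, 7/10 = 70% stopped. The number of such withdrawals is uncertain. SAP 5.1 withdraws non-responders, while Protocol 6.2.1.1 keeps subjects who restart PEG-ADA in follow-up. These passages need to be reconciled.

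**The case against.** The strongest reply is that the section does not hide non-stoppers. The by-visit and 12/18/24-month counts are unconditional, and the second is net of restarts. A reader shown a median of 14 months would also see how many of the ten had stopped. A reader might infer that these children are left out of the IgRT analysis altogether; the documents do not support that. They are missing from the time statistic only. Even that is inferred from the formula, since the SAP never states an exclusion. This part of the reply stands and limits the harm. It does not repair a median that is wrong for the cohort, and the section states no denominator for the percentages.

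The conditional clause also has a sensible reading: use the curve when some children have not stopped. That may be the intention, but it is not written, and step 3 shows that the curve would still need a rule for withdrawn failures.

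Three other strong readings fail:
- The statistic does not always understate. If all ten stop, the gap is zero.
- Nothing in the documents makes IgRT use the main sign of B-cell recovery. B-cell reconstitution and tetanus response are separate secondary endpoints.
- PEG-ADA shares the wording but hardly the bias. It is "discontinued at Day 30 (-3/+15) after the transplant", so most treated children should have a stop date that reflects the schedule. A restart counts as an event in event-free survival (SAP 8.3.1.3).

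Finally, the study plans no formal comparisons, and the endpoint is descriptive with ten subjects. That lowers the stakes, but a descriptive figure should still describe the treated cohort.

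**Conclusion.** The point holds for IgRT in SAP 8.3.2.2. The one mandatory time statistic is conditional on having stopped, and it errs towards faster recovery whenever some children have not stopped. The direction follows from the definition. The size rests on assumed stop times: under the Weibull assumption it runs from about 0% to 4% of the median (true median 9 months) to 37% to 44% (true median 24 months). The documents give nothing with which to place this trial within that range.

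The optional Kaplan-Meier estimate is not a full remedy. Its overstatement of 8 or 18 percentage points in step 3 assumes one or two month-6 withdrawals while on IgRT.

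This is a worthwhile correction to a secondary descriptive endpoint. It does not touch the primary endpoints.

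**What to change.** In SAP 8.3.2.2:
- Remove the conditional clause, and make a time-to-event summary over all treated subjects on IgRT at infusion the stated analysis.
- Use the cumulative incidence of stopping, with death and withdrawal for treatment failure or rescue HSCT as competing events, so that these children count as not having stopped. Censor only subjects still in follow-up at the data cut.
- Report the median, or state that it was not reached.
- Keep descriptive statistics of stop times only if they are labelled as being among those who stopped, n of N.
- Define the stop as the final one without later restart, to match the existing 12/18/24-month summary. Protocol 6.2.1.1 allows IgRT to be reintroduced, and the time variable has no rule for that.

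Keep the existing by-visit and fixed-time proportions. The wording in SAP 8.3.3.1 can be aligned for consistency, though little change in the PEG-ADA result is to be expected.

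The cost is a few lines of SAP text and one standard SAS procedure, with no new data. The reported figure may be less favourable, or may not be reached.

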- Assessment of the success of treatment at the subject level (“responder analysis”) at 6 months post OTL-101 infusion, by evaluating:
 - a) Evidence of erythrocyte ADA enzyme activity above baseline/pre-treatment level (>0 Units),
 - b) Evidence of immune reconstitution (absolute number of CD3 cells $\geq 200/\text{mm}^3$),
 - c) Detectable gene-marked granulocytes by differential polymerase chain reaction (dPCR)/qPCR ($\geq 1/10,000$ cells).

If there is no evidence of hematopoietic reconstitution, subjects will require PEG-ADA and/or allogenic HSCT, if available and deemed appropriate by the Investigator. The definition applied for lack of hematopoietic reconstitution is the failure to meet ALL three criteria listed above (a-c). Any subject not meeting any of these three criteria will be deemed a treatment failure and should be withdrawn from the study as described in [Section 3.6.1](#).

- Hematology and biochemistry panels,
- RCL assay in PBMC,
- Serum to be banked for possible Western blot testing for RCL (testing performed if the RCL assay in PBMC returns a positive result),
- Monitoring for leukemia (by nrLAM-PR) if the criteria for triggering nrLAM-PCR are fulfilled. A blood sample will be taken unless clinical/hematologic findings indicate potential leukoproliferation, whereby a bone marrow sample will be required,
- Monitoring for severe infections and/or opportunistic infectious episodes at each study visit,
- Vector integration analysis,
- Immune function testing:
 - o Determination of absolute numbers of CD3+, CD4+ and CD8+ T-lymphocytes, CD19+ B-lymphocytes and CD56/CD16+ (or CD56+/CD3-) NK cells, CD4+/CD45RA+ (naïve) and CD4+/CD45RO+ (memory) T cells,
 - o T-cell proliferative responses to PHA,
 - o Measurement of serum immunoglobulin levels (IgG, IgA, IgM) if not receiving immunoglobulins,

PROTOCOL AMENDMENT 4: VERSION 5.0, 28 MARCH 2018

PAGE 56/130

- TREC,
- TCR V β usage,
- Gene transduction/expression;
 - Measurement of the proportion of cells containing the inserted *ADA gene* in PBMC and granulocytes and/or lineage-sorted cells,
 - Measurement of ADA expression in erythrocytes by ADA enzymatic assay and deoxyadenine nucleotides in RBC.

Month 9 (Visit 8 - +/- 2 weeks)

- Physical examination, vital signs, height, weight and interval history (including routine review of systems, including infectious symptoms (e.g., fever), AEs and concomitant medications),

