- Assessment of re-initiation of PEG-ADA therapy and use of IgG replacement therapy will be documented. Please note: subjects should have discontinued PEG-ADA treatment at Visit 4 (Month 1/Day 30),
- Hematology and biochemistry panels,
- Monitoring for severe infections and/or opportunistic infectious episodes at each study visit,
- Immune function testing;
 - Determination of absolute numbers of CD3+, CD4+ and CD8+ T-lymphocytes, CD19+ B-lymphocytes and CD56/CD16+ (or CD56+/CD3-) NK cells, CD4+/CD45RA+ (naïve) and CD4+/CD45RO+ (memory) T cells;
 - T-cell proliferative responses to PHA,
 - Serum immunoglobulin (IgG, IgA, IgM),
- Gene transduction/expression;
 - Measurement of ADA expression in erythrocytes by ADA enzymatic assay and deoxyadenine nucleotides in RBC.

Month 12 (Visit 9 - +/- 4 weeks)

- Physical examination, vital signs, height, weight and interval history (including routine review of systems, including infectious symptoms (e.g., fever), AEs and concomitant medications),
- Evaluation of quality of life using the Karnofsky/Lansky scale and questions relevant to general well-being, school attendance, and ability to practice sports, respectively,
- Assessment of re-initiation of PEG-ADA therapy and use of IgG replacement therapy will be documented. Please note: subjects should have discontinued PEG-ADA treatment at Visit 4 (Month 1/Day 30),
- Hematology and biochemistry panels,
- RCL assay in PBMC,

- Serum to be banked for possible Western blot testing for RCL (testing performed if the RCL assay in PBMC returns a positive result),
- Vector integration analysis,
- Monitoring for leukemia (by nrLAM-PR) if the criteria for triggering nrLAM-PCR are fulfilled. A blood sample will be taken unless clinical/hematologic findings indicate potential leukoproliferation, whereby a bone marrow sample will be required,
- Monitoring for severe infections and/or opportunistic infectious episodes at each study visit,
- Immune function testing:
 - o Determination of absolute numbers of CD3+, CD4+ and CD8+ T-lymphocytes, CD19+ B-lymphocytes and CD56/CD16+ (or CD56+/CD3-) NK cells, CD4+/CD45RA+ (naïve) and CD4+/CD45RO+ (memory) T cells;
 - o T-cell proliferative responses to PHA,
 - o Measurement of serum immunoglobulin levels (IgG, IgA, IgM) if not receiving immunoglobulins,
 - o Measurement of specific antibodies to tetanus toxoid only if subjects have stopped immunoglobulin replacement and have received tetanus vaccination,
 - o TREC,
 - o TCR V β usage,

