- Subjects will continue to receive prophylactic antifungal medication, such as oral nystatin or fluconazole in standard doses. This can be discontinued when CD4 >200/ μ l.
- Additional or alternative antibiotics may be administered, based on clinical care considerations (these will be recorded as concomitant medications).

Immunoglobulin Replacement Therapy

Immunoglobulin G infusions will be given according to institutional standards (e.g., 400 to 600 mg/kg q 3-4 weeks), and in general are expected to be maintained until through IgG levels of at least 500 mg/dL. Indications for considering the discontinuation of immunoglobulin replacement therapy include: absolute CD4+ >200, absolute B cell >100/ μ l, IgA or IgM > lower limit of normal for age or gene marking >1% detectable in B cells. IgG levels will be checked monthly to document their independence from IgG infusions. If, at least 3 months later, IgG levels are >300 mg/dL, the subject will undergo vaccination, which will include three doses of tetanus and two to three doses of 13-valent pneumococcal vaccine, according to published clinical standards ([Griffith2009](#)). Immunoglobulin G antibodies to tetanus will be determined at least 4 weeks after completing the three vaccinations.

Pre-vaccination and post-vaccination titers will be measured and recorded in the eCRF. Until protective responses to the vaccines have been documented, the subject should remain on antibiotic prophylaxis. If the subject fails to mount a protective antibody response to tetanus, as determined by a titer of anti-tetanus antibodies >0.15 IU/ml at least 4 weeks after the third immunization, IgG replacement therapy will be reintroduced. This therapy will also be resumed in the event of a subject developing an infection that requires hospitalization while off-IgG and on antibiotic prophylaxis.

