9.6.3 Baseline Characteristics

The following information collected at baseline will be presented:

- Demographics (Age, Gender, etc.),
- Method of diagnosis,
- Previous HSCT including: date, transplant cells, donor type and outcome,
- Previous PEG-ADA ERT (and duration of treatment),
- Previous or current immunoglobulin therapy,
- Listing of relevant medical history, including infections.

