5. Immune function will be assessed by absolute numbers of CD3+, CD4+ and CD8+ T-lymphocytes, CD19+ B-lymphocytes and CD56+/CD16+ (or CD56+/CD3-) NK cells, CD4+/CD45RA+ (naïve) and CD4+/CD45RO+ (memory) T cells, TREC levels, TCR V β usage, lymphocyte response to PHA (if sufficient cells), and serum immunoglobulin (IgG, IgA, IgM).
6. If IgG treatment is stopped, immunoglobulin levels will be required every month for the first 3 month after discontinuation. This is to ensure IgG levels hold before commencing vaccinations as per standard institute protocols.
7. A blood sample will be taken unless clinical/hematologic findings indicate potential leukoproliferation, whereby a bone marrow sample will be required. In addition to the time points specified in this table, this assessment should be performed if the nrLAM-PCR criteria is fulfilled (see Section **Error! Reference source not found.**).
8. Responder assessment includes: erythrocyte ADA enzyme activity, immune reconstitution, and gene-marked granulocytes as described in Section **Error! Reference source not found.**

Abbreviations: ADA=adenosine deaminase, ALP=alkaline phosphatase, ALT=alanine aminotransferase, AST=aspartate aminotransferase, eCRF=electronic case report form, ET=early termination, IgA=immunoglobulin A, IgG=immunoglobulin G, IgM=immunoglobulin M, N/A=not applicable, NK=natural killer, PBMC=peripheral blood mononuclear cells, PCR=polymerase chain reaction, PEG= polyethylene-glycol, PHA= Phytohemagglutinin, QoL=quality of life, RBC=red blood cell, RCL= Replication Competent Lentivirus, TCR= T-cell receptor, TREC= T-cell receptor excision circle.

4 Study Objectives

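### SAP 8.3.2.2 summarises serum IgG by visit without regard to immunoglobulin replacement, so the table and median plot mix infused with endogenous IgG; the documents also disagree on who is sampled at Months 6 and 12

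*SAP*

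**What the plan says.** **Analysis.** SAP 8.3.2.2 says that "serum immunoglobulin levels (IgG, IgA and IgM) will be measured at each visit" and then that "Levels of IgG, IgA and IgM and changes from baseline will be summarized by visit using descriptive statistics". It adds plots of the median and range over time, and individual plots against age-dependent normal ranges. Replacement status is not used as a stratum, an exclusion or a flag in any of these.

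**Sampling.** Protocol 5.1.7 words the test at Months 6 and 12 as "Measurement of serum immunoglobulin levels (IgG, IgA, IgM) if not receiving immunoglobulins". At Months 1, 3, 9, 18 and 24 it lists "Serum immunoglobulin (IgG, IgA, IgM") with no condition, and Protocol 5.1.3 does the same at baseline. Table 2 footnote 5, identical in protocol and SAP, defines the immune function panel as including "lymphocyte response to PHA (if sufficient cells), and serum immunoglobulin (IgG, IgA, IgM"), also with no condition. Table 2 marks that panel at Months 6 and 12.

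**Replacement.** Protocol 9.6.3 expects subjects to have "Previous or current immunoglobulin therapy" at baseline. Protocol 6.2.1.1 says that infusions "in general are expected to be maintained until through IgG levels of at least 500 mg/dL". After stopping, IgG is checked monthly, and a level above 300 mg/dL at least 3 months later lets the subject go on to vaccination. One listed indication for considering stopping is "IgA or IgM > lower limit of normal for age or gene marking >1% detectable in B cells".

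**Role of the endpoint.** Protocol 3.2.4, 7.1.3 and 9.3.3 list serum immunoglobulin levels under immune reconstitution, as exploratory and descriptive endpoints.

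**The concern.** In a subject on replacement, measured IgG includes infused IgG and does not by itself show B-cell recovery. The protocol accepts this elsewhere. Tetanus antibodies are measured only in subjects who have stopped replacement (Protocol 5.1.7, SAP 8.3.2.5), and independence from infusions is judged only after an interval of at least 3 months. SAP 8.3.2.2 does not carry this over to total IgG.

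Two things follow. First, the by-visit summary depends on how many subjects happen to be on infusions at each visit, and its direction can mislead. A subject who comes off infusions can show a fall, while one who stays dependent shows a stable level. Protocol 6.2.1.1 also brings IgG back after a failed tetanus response, so a level could rise for that reason.

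Second, if Protocol 5.1.7 is followed at Months 6 and 12, those two points describe a different group from the points on either side. This bears on the first analysis. SAP section 6 triggers it when at least 5 subjects have reached 6 months, and says secondary and exploratory endpoints will be compared with the fresh-formulation study. The Month 6 immunoglobulin summary would then rest on whichever of those few subjects are off replacement.

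**Working it through.** The plan gives no figure of its own here, so there is nothing to reproduce. The check is a reading of the passages plus an illustration.

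**1. Who is sampled at Months 6 and 12**

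| Source | Condition |
|---|---|
| Protocol 5.1.7, Months 6 and 12 | only if off immunoglobulins |
| Protocol 5.1.7, Months 1, 3, 9, 18, 24 | none |
| Table 2 footnote 5 (protocol and SAP) | none |
| SAP 8.3.2.2 | none; every visit |

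The sources conflict. Footnote 5 may be a generic panel list, since it includes TREC, which 5.1.7 omits at Months 1, 3 and 9. That does not settle the matter, because the SAP sentence is explicit. Under either reading the summary has a problem. If everyone is sampled, infused IgG is mixed in at every visit. If 5.1.7 holds, it is mixed in at the other visits, and Months 6 and 12 cover a subset.

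**2. Change in one subject**

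Inputs from Protocol 6.2.1.1: 500 mg/dL on infusions, and just above 300 (301) mg/dL off them. The 500 sentence is loosely worded; I use it as an assumed on-infusion level.

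- Becomes independent: 301 - 500 = -199 mg/dL.
- Stays on infusions at 500: 500 - 500 = 0.

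Range over assumed levels:

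| On infusions | Off infusions | Change |
|---|---|---|
| 500 | 500 | 0 |
| 500 | 400 | -100 |
| 500 | 301 | -199 |
| 800 | 301 | -499 |

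**3. Effect on the visit summary**

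Take N = 10 (Protocol 9.4), everyone at 500 on infusions at baseline, and 301 once off. The number off replacement, k, is assumed to be 0, 2, 4, 4, 6 and 8 at Months 3, 6, 9, 12, 18 and 24. Sampling follows Protocol 5.1.7. Where all are sampled, mean = ((10 - k) × 500 + k × 301) / 10. Where only off-replacement subjects are sampled, mean = 301 with n = k.

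| Month | Sampled | n | Mean | Change | Median |
|---|---|---|---|---|---|
| 3 | all | 10 | 500.0 | 0 | 500 |
| 6 | off only | 2 | 301.0 | -199.0 | 301 |
| 9 | all | 10 | 420.4 | -79.6 | 500 |
| 12 | off only | 4 | 301.0 | -199.0 | 301 |
| 18 | all | 10 | 380.6 | -119.4 | 301 |
| 24 | all | 10 | 340.8 | -159.2 | 301 |

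For example, Month 9: (6 × 500 + 4 × 301) / 10 = 4204 / 10 = 420.4. The median there is 500 because six of the ten values are 500.

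The saw-tooth comes from who is sampled. If all ten were sampled at Months 6 and 12, the means would be 460.2 (k = 2) and 420.4 (k = 4). The curve would then decline steadily as more subjects became independent, which is still the wrong direction for a recovery measure.

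**The case against.** The strongest reply is that a reader of the full output is unlikely to be misled. SAP 8.3.2.2 also gives the number on replacement by visit, time to cessation, and the number durably stopped at 12, 18 and 24 months. With about ten subjects, the individual plots show every trajectory. Table 2 footnote 6 adds monthly levels for 3 months after stopping. The SAP's own immune reconstitution analysis (8.3.2.6) uses lymphocyte subsets, including CD19+ B cells, and antibody function is judged by tetanus response in subjects off replacement. The levels are descriptive and feed no decision rule.

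Most of that stands and limits the importance of the point. It does not remove it. None of these items separates infused from endogenous IgG in the table or the median plot, and an unflagged infused value on an individual plot can simply look normal.

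Three stronger readings are tempting but unsupported:

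- A reader might infer that Months 6 and 12 definitely include only subjects off replacement. Only Protocol 5.1.7 says so, and two other places disagree.
- A reader might infer that the plan equates infused IgG with recovery. The SAP does not say this. It reports the levels under replacement use, and the link comes from the protocol's exploratory endpoint list.
- A reader might infer that success must appear as a fall. It need not: the change is 0 when endogenous IgG matches the earlier infused level. A level above 300 mg/dL only permits vaccination and is not itself treatment success.

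**Conclusion.** The point holds in a limited form. As written, SAP 8.3.2.2 produces a by-visit IgG table and median plot that mix infused and endogenous IgG, so the time course cannot be read as B-cell recovery. At the protocol's thresholds the distortion is -199 mg/dL for a subject who becomes independent, against 0 for one who stays on infusions. Over the assumed levels it runs from 0 to -499. These sizes rest on the assumed on- and off-infusion levels, and the visit pattern rests on assumed numbers off replacement; the documents give neither.

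The Month 6 and 12 sampling is an unresolved contradiction. If 5.1.7 is followed, those summaries describe only subjects off replacement. IgA and IgM are then also missing at those visits for subjects still on replacement, although the protocol lists them among the indications for considering stopping it.

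The effect is confined to a descriptive, non-primary summary and is partly mitigated. The change is nonetheless worth making, because it is cheap and the same summaries are to be compared with the fresh-formulation study.

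**What to change.** In SAP 8.3.2.2:

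- Present IgG levels and median plots at each visit in two groups: on replacement or within 3 months of the last infusion, and at least 3 months off. Show the number in each group. The 3 months is the protocol's own interval.
- Flag on-replacement values on the individual plots.
- Do not present IgG change from an on-replacement baseline as reconstitution.
- Keep IgA and IgM summaries for all sampled subjects, with the number shown.

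Reporting only subjects at least 3 months off is not recommended. It would make every visit a selected subset of changing size, which is the difficulty that 5.1.7 creates at Months 6 and 12.

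Separately, reconcile Protocol 5.1.7 at Months 6 and 12 with Table 2 footnote 5 and the SAP on who is sampled. That decision has to allow for the blood-volume limits and test ranking in 5.1.7, so it may be more than an editorial correction.

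**Cost.** The SAP change is wording and programming. Table 2 already records immunoglobulin therapy at each follow-up visit, and the SAP already uses stop dates from the concomitant medication form. The downside is smaller groups per visit, in a study of ten.
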